This is an open-label single-arm pilot clinical trial testing the feasibility, acceptability, and effects of a 4-week EC substitution intervention in 30 current smokers. Approach: Participants will be asked to switch from CC to the NJOY ACE electronic cigarette (EC) for 4 weeks. They will receive counseling to develop a plan to fully substitute CC for EC and to increase EC adherence. Follow-up assessment at 8 weeks will determine whether participants continue to use EC, return to cigarette smoking, or use both products. The primary outcomes are study feasibility (participant enrollment and retention) and change in cigarettes per day from baseline to week 4 (primary outcome). Secondary outcomes include change in exposure biomarkers (expired air CO, urine cotinine and anabasine) from baseline to week 4, product acceptability and tolerability (days of EC use, adverse events) and change in CC and EC use after EC provision ends. At the end of EC provision (week 4), we will conduct exploratory qualitative exit interviews in a purposive subsample to explore their experiences participating in the study and switching from CCs to ECs.

4. Subject Selection

Inclusion Criteria

- a) Participants in the Screen Assist study (IRB#2018P000539) who self-reported smoking cigarettes at the end of the study and were asked to complete a subsequent Screen Assist survey to ascertain their potential interest in a research study to test the effects of switching from CC to EC. Individuals who expressed interest in a future research study about EC on that survey are eligible for this study.
- b) Smoked ≥ 5 cigarettes/day in past month
- c) Willingness to try switching to EC for 4 weeks
- d) Own a mobile telephone
- e) Smoking status at study entry confirmed by breath carbon monoxide (CO) ≥ 6 ppm
- f) English speaking
- g) Willingness to travel to the MGH main campus for 3 in-person visits

Exclusion Criteria

- a) Plan to quit smoking and have set a quit date in the next 30 days
- b) Current EC use on >2 days in the past 30 days
- c) Hospitalization for acute coronary syndrome, unstable angina, CHF, stroke, pneumonia or COPD/asthma exacerbation in the past 1 month
- d) Be willing not to smoke marijuana in the 24h before each study visit

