There is a possible direct benefit to participants. Patients will be instructed to reduce their combustible daily cigarette use and to substitute e-cigarette use for cigarette use. This aims to facilitate reductions in cigarettes smoked per day, reduced tobacco smoke exposure and eventual increase in health benefits (e.g., improvement in dyspnea). Even if e-cigarettes are found to not reduce exposure to toxins, cigarettes per day, or if respiratory symptoms were to worsen with their use (which is not anticipated), this study will still provide valuable data about the need for patients to avoid e-cigarette products. The data from this trial will be clinically informative and inform policies on regulating and marketing e-cigarettes. A systematic review of randomized controlled trials indicates that e-cigarettes are more effective than nicotine replacement products for helping cigarettes smokers to quit smoking.¹⁰ Quitting smoking is associated with a rapid reduction in tobacco-related health risks, even in older individuals who have smoked enough to qualify for lung cancer screening, as our study population does.⁴¹

In the qualitative interview, participants will also discuss their attempts to reduce their cigarette use and barriers and facilitators to e-cigarette substitution which may be useful for increasing participants' awareness of their cigarette use, what maintains use, and obstacles to stopping use which could be useful for eventual cessation of cigarette use.

9. Statistical Analysis

Aim: Assess the feasibility, acceptability, and short-term effects of providing ECs for 4 weeks to encourage switching from cigarettes to e-cigarettes by individuals who did not quit after smoking cessation treatment provided in the context of LCS and do not currently plan to quit.

Hypothesis 1: (i) ≥ 40% of eligible smokers who are offered trial enrollment. (ii) ≥ 75% of enrollees complete the trial

Primary Outcomes H1: Study enrollment (% screened of those who completed our study 1 survey, % eligible of those screened; % enrolled of those screened eligible); retention (% of patients who complete the trial, defined as completing the final follow-up assessment and >50% of the study visits). We will also document reasons for ineligibility and exclusion to inform future trial protocols.

Analysis H1: Descriptive statistics using data from study recruitment and enrollment records will test hypotheses.

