H2b: Participants will report fewer CPD at the end of the 4-week EC switch period, relative to their baseline values.

Primary Outcome H2: Change in mean cigarettes smoked per day (CPD) between baseline and 4 weeks.

Analyses H2: Paired sample t-tests will be used to compare mean differences in past 7-day CC use from BL to Week 4. Linear mixed models will also be used to test differences in CPD and CO levels over the study period (using data from all observed time points observed). Primary analysis will be conducted among completers and multiple imputation will be used for a sensitivity analysis.

Additional Planned Analyses: Analyses of other secondary outcomes will include EC acceptability measures and changes from baseline to week 4 in the levels of: EC use days, levels of biomarkers of exposure (CO, anabasine, cotinine). The qualitative interviews will be audio-recorded, transcribed, and iteratively analyzed using the framework method of content analysis (both inductive and deductive) in Dedoose 8.3 qualitative software. The trained research assistants will separately review each transcript and develop a coding framework. The coders will meet weekly with the PIs to review results for agreement.

Power: If 40% (n=30) of 75 screened eligible subjects agree to participate, the width of the 95% CI will be limited to 11.1% on each side. If at least 24 of the 30 subjects complete the study, the width of the 95% CI will be limited to 14.7% on each side. Hyp 2b: Participants will report fewer CPD after 4 weeks of EC provision relative to their baseline values. Results from PI [name]'s recent study⁴² found a significant reduction in mean CPD in the EC arm (N=18) from 14.8 cigarettes per day to 4.4 in week 4 (Change SD: 3.81) (p-value <0.01) (Cohen's d=1.6). With a sample size of 30 and a 25% attrition rate, we expect at least 24 of the 30 subjects will provide data on CPD reduction. The study will have 80% power to detect a more conservative Cohen's d of 0.60 with a two-sided type-I error of 5%. A Cohen's d of 0.60 will translate into a mean change of 3 CPD (SD of change=5).

10. Monitoring and Quality Assurance

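### The power paragraph pairs 25% attrition with 24 evaluable participants, but 25% of 30 leaves 22–23, where power at d = 0.60 is 76.5–78.5% rather than 80%

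*Combined protocol and SAP*

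**What the plan says.** Section 3 describes a "4-week EC substitution intervention in 30 current smokers", and change in CPD from baseline to week 4 is a primary outcome. In section 9, the H2 analysis is a paired t-test on past-7-day cigarette use, and "Primary analysis will be conducted among completers", with multiple imputation only as a sensitivity analysis.

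The Power paragraph of section 9 gives the sample size reasoning: "With a sample size of 30 and a 25% attrition rate, we expect at least 24 of the 30 subjects will provide data". The data meant there are those for the CPD outcome. It continues: "The study will have 80% power to detect a more conservative Cohen's d of 0.60 with a two-sided type-I error of 5" (per cent), and equates d = 0.60 with a mean change of 3 CPD and an SD of change of 5.

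Three other statements bear on this:

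- Hypothesis 1(ii) in section 9 sets retention at or above the level in "75% of enrollees complete the trial". Section 2 words the same target as strictly above 75%.
- For 24 completers out of 30, the Power paragraph says "the width of the 95% CI will be limited to 14.7% on each side".
- For the prior study behind the effect size, it reports a fall "from 14.8 cigarettes per day to 4.4 in week 4 (Change SD: 3.81) (p-value <0.01) (Cohen's d=1.6").

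**The concern.** The attrition rate and the evaluable number stand in one sentence and cannot both be right. Rounding does not turn 22.5 into 24, and calling 24 a minimum makes the gap harder to explain. The number matters because the next sentence's power claim depends on it, and because the primary analysis uses completers only, so each lost participant reduces the analysed sample.

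The paragraph therefore promises 80% power for a primary outcome at an attrition rate where the planned analysis does not reach it. It also carries two retention assumptions, 75% and 80%, without saying which one the design rests on. Section 4's background text (end of section 1) says the pilot will inform a fully powered trial, so its planning assumptions should be readable.

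**Working it through.** **Inputs, all from the plan.** N = 30; attrition 25%; evaluable 24; d = 0.60 (3 CPD ÷ SD 5); two-sided 5%; paired t-test among completers.

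**Attrition.**

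- 30 × (1 − 0.25) = 22.5, so 22 or 23 participants.
- 24 ÷ 30 = 80% retained, which is 20% attrition.
- To keep 24 at 25% attrition, enrolment would have to be 24 ÷ 0.75 = 32.
- 24 × 1.25 is exactly 30. The 30 may therefore have come from multiplying by 1 + 0.25 instead of dividing by 1 − 0.25. That is an inference; the plan does not say so.

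**Power.** The paired t-test has n − 1 degrees of freedom and noncentrality d√n, and power comes from the noncentral t distribution. The plan's own figure reproduces at n = 24:

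| Evaluable n | d√n | Two-sided 5% critical t | Power at d = 0.60 | d for 80% power | CPD at SD 5 |
|---|---|---|---|---|---|
| 24 | 2.939 | 2.069 | 80.4% | 0.597 | 2.99 |
| 23 | 2.877 | 2.074 | 78.5% | 0.611 | 3.06 |
| 22 | 2.814 | 2.080 | 76.5% | 0.626 | 3.13 |

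So 24 is the smallest n that gives 80%, with no slack for the one or two participants that 25% attrition would remove.

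**Allowing for chance in dropout.** This assumes that participants drop out independently, which the plan does not state. With retention 75%, the number of completers is Binomial(30, 0.75): the chance of 24 or more is 35% and average power is 77.1%. With retention 80%, these are 61% and 80.0%.

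**Against the retention hypothesis.** 23 ÷ 30 = 76.7% meets the 75% target in either wording, with power 78.5%. 22 ÷ 30 = 73.3% does not meet it.

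**Two other figures in the paragraph, neither of which enters the power calculation.**

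- Prior-study effect: (14.8 − 4.4) ÷ 3.81 = 10.4 ÷ 3.81 = 2.73, not 1.6. A d of 1.6 would need a standardiser of 10.4 ÷ 1.6 = 6.5, which is not named.
- Confidence half-widths: for 30 of 75, the Wald formula gives 1.96 × √(0.4 × 0.6 ÷ 75) = 11.1%, as stated. For 24 of 30, the same formula gives 1.96 × √(0.8 × 0.2 ÷ 30) = 14.3%, not 14.7%. Average half-widths by other methods are Wilson 13.9%, Agresti–Coull 14.3%, Jeffreys 13.9% and Clopper–Pearson 15.4%. None gives 14.7%.

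**The case against.** The strongest objection is that retention and availability of CPD data are different quantities. Section 9 defines trial completion by the final follow-up assessment plus more than half the visits, and the last contact is the week 8 call. The CPD outcome is measured at week 4. Someone lost between weeks 4 and 8 counts against retention but can still supply a CPD change, and the plan does not say at which week a completer is defined for the H2 analysis. On that reading, 25% trial attrition and 24 participants with CPD data could coexist. It does not rescue the text, because the sentence applies the 25% directly to participants who provide CPD data, and no lower loss rate to week 4 is given.

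A second objection is that a normal approximation needs only 22 participants (80.4%). That is not the planned test, and it overstates power at this sample size.

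A third is that the consequence is slight, and this stands. The trial is a 30-person single-arm pilot with feasibility also primary. The plan calls d = 0.60 conservative, and at d = 1.6 power with 22 participants would exceed 99.9%. Mixed models using all observed time points are planned as well. It is also fair that only the 1.5-point shortfall (n = 23) goes with meeting the retention target; the 3.5-point shortfall (n = 22) goes with missing it. A follow-on trial would rely mainly on the retention this pilot observes.

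On the two side figures, the cited study is not available here, so d = 1.6 may rest on another standardiser. The plan names no interval method, so the 14.3% rests on the Wald formula matching the neighbouring figure.

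**Conclusion.** The concern holds. As written, 25% attrition from 30 does not leave 24 participants with CPD data, and the 80% power claim needs all 24. At 22–23 evaluable, power for d = 0.60 is 76.5–78.5%, a loss of 1.5 to 3.5 points; equivalently, the effect detectable with 80% power is d = 0.61–0.63, about 3.1 CPD in place of 3.0.

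This rests on the test the plan names, its two-sided 5% level, its SD of change of 5, and reading the 25% as loss of CPD data, which is what the sentence says. The error lies in the justification of a primary outcome and should be corrected, but it does not undermine the design or call for more participants. The d of 1.6 is either wrong or lacks a named standardiser. The 14.7% does not follow from the method that reproduces its neighbour.

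**What to change.** Keep N = 30 and make one of two edits to the Power paragraph:

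- **State 20% attrition**, with 24 evaluable and 80% power for d = 0.60; or
- **Keep 25%**, which matches the 75% retention hypothesis, state 22–23 evaluable, and give power as about 77–79% for d = 0.60, or 80% power for d of 0.61–0.63 (about 3.1 CPD at SD 5).

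If the authors meant that week 4 data would be more complete than trial completion, the first edit is the place to say so: give the assumed loss to week 4 separately and define completers for the H2 analysis.

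In the same edit, correct the prior-study d or SD, or name the standardiser behind 1.6. Change 14.7% to 14.3% for 24 of 30, or name the interval method if it is not Wald.

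The cost is rewording one paragraph, with no change to sample size, visits or analysis. If 25% is kept, the stated power falls by 1.5 to 3.5 points.
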